## Protocol summary

Protocol number	CMIJ821X2201
Full Title	A multi-center, randomized, subject and investigator-blinded, placebo-controlled, active comparator, parallel-group proof of concept study to evaluate the efficacy, safety, tolerability, and pharmacokinetics of MIJ821 in patients with treatment-resistant depression
Brief title	Study of efficacy and safety of MIJ821 in treatment-resistant depression patients.
Sponsor and Clinical Phase	Novartis
Investigation type	Drug
Study type	Interventional
Purpose and rationale	
The main purpose of this non-confirmatory study is to evaluate the clinical responses of MIJ821 in patients suffering from treatment-resistant depression assessed by the Montgomery Åsberg Depression Rating Scale (Montgomery and Asberg 1979).
 
Furthermore it is expected that this study will guide the future clinical trials with MIJ821 in treatment of resistant depression.

Primary Objective(s)	The primary objective of this study is to assess the efficacy of MIJ821 in treatment-resistant depression at 24 hours after the start of infusion. The measure will be conducted through MADRS total score, 24 hours after the start of first infusion compared to the baseline assessment.
Secondary Objectives	
To assess the efficacy of MIJ821 in treatment-resistant depression by 1) evaluating the percentage of treatment response (>50% improvement in MADRS) at 24 hours, 48 hours (if applicable) and 6 weeks after the start of first infusion 2) evaluating the percentage of remission (MADRS <7) at 24 hours, 48 hours (if applicable) and 6 weeks after the start of first infusion; 3) evaluating the CGI-I and CGI-S scores at 24 hours, 48 hours (if applicable), and 6 weeks after the start of first infusion.
 
To assess the impact of MIJ821 on suicidality.
 
To assess the MIJ821 pharmacokinetics in plasma.
 
To assess the most effective dose and dosing regimen.
 
To assess the safety and tolerability of weekly and bi-weekly infusions of MIJ821.
 
To assess the efficacy in melancholic subtype of depression.
 
To assess the risk of mania induction.
 
To assess the efficacy of MIJ821 for mixed mood symptoms.
 
To assess the efficacy of MIJ821 for anxiety symptoms.
 
To assess the impact of mixed mood symptoms, melancholia, and anxiety as predictors of treatment response to MIJ821.

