
 
To assess risk of mania induction.
 
To assess efficacy in the melancholic subtype of depression.
 
To assess safety and tolerability, especially dissociative side effects.
 
To assess most effective dose and dosing regimen.
 
To assess MIJ821 pharmacokinetics in plasma.
 
To assess impact of MIJ821 on suicidality.
 
To assess efficacy of MIJ821 on measures of response and remission
 
To assess efficacy of MIJ821 for mixed mood symptoms.
 
To assess efficacy of MIJ821 for anxiety symptoms.
 
	
 
Young Mania Rating Scale at 24 hours, 48 hours (if applicable) and 6 weeks post-dose.
 
Bech-Rafaelsen Melancholia and CORE scale change from baseline to 24 hours, 48 hours (if applicable) and 6 weeks post-dose.
 
Incidence of adverse event Dissociative rating scales (Clinician-Administered Dissociative States Scale, and Dissociative Experiences Scale) change from baseline to 24 hours, 48 hours (if applicable) and 6 weeks post-dose.
 
Montgomery Asberg Depression Rating Scale score at 6 weeks.
 
PK properties of MIJ821 in plasma described by AUClast, AUC0-24h, Cmax, Tmax (parameters not limited)
 
Sheehan Suicidality Tracking Scale changes from baseline at 24 hours, 48 hours (if applicable), and 6 weeks after the start of first infusion.
 
% treatment response (>50% improvement in MADRS) at 24 hours, 48 hours (if applicable), and 6 weeks after the start of first infusion. % treatment remission (MADRS<7) at 24 hours, 48 hours (if applicable), and 6 weeks after the start of first infusion CGI-S and CGI-I scores at 24 hours, 48 hours (if applicable), and 6 weeks after the start of first infusion
 
Koukopoulos Mixed Depression Rating Scale change from baseline to 24 hours, 48 hours, and 6 weeks after the start of first infusion.
 
Hamilton Anxiety Scale change from baseline to 24 hours, 48 hours (if applicable), and 6 weeks after the start of first infusion
 

Objective(s)	Endpoint(s)

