### **3 Study design**

This is a non-confirmatory, multi-center, 6-treatment arm in the European countries and 5-treatment arm in the USA (no ketamine arm), randomized, subject and investigator blinded, parallel group, placebo controlled study in treatment-resistant depression patients. The study will randomize approximately 66 Subjects and while the study design utilizes an outpatient visit schedule, the study allows for the inclusion of subjects seeking treatment for their disease from both an 'inpatient' or 'outpatient' clinic setting.

A screening period of maximum 4 weeks will be used to assess eligibility. Patients who meet the eligibility criteria at screening will proceed to baseline evaluations on Day-1 or Day 1. All baseline safety evaluation results must be available prior to randomization. At the baseline visit, eligible subjects will be randomized to one of the treatment arms. Randomized subjects will enter a 36- day treatment period, receiving at each treatment visit, a 40-minute infusion with a safety observation period of 2-4 hours (i.e. a minimum of 2 hours) post the start of

infusion. If the subject reports no dissociative symptoms and no suicidal symptoms, the subject will be allowed to leave the clinical treatment setting. Visits to assess efficacy and safety are scheduled at 24 hours, 48 hours (if applicable) and every week during the treatment period. If 48 hour visit (V103) is conducted, then all assessments should be completed. The assessment to address the primary objective will be performed at 24 hour post-dose. Safety assessments will include physical examinations, ECGs, vital signs, standard clinical laboratory evaluations (hematology, blood chemistry, and urinalysis), adverse event and serious adverse event monitoring. At the conclusion of the treatment period (Day 1 - Day 36), subjects will enter a 5-week follow up period consisting of two follow visits approximately 1 week (Day 43) and 3 weeks (Day 57) after the last study drug administration and an end of study completion visit (Day 71) The total duration for each subject in the study is maximum 14-weeks including screening and baseline. No interim analysis is planned. The study design is summarized in [Figure 3-1](#) below for the European countries (same study design without the ketamine arm in the USA).

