### **12.5.2 Safety endpoints**

For all safety analyses, the safety set will be used. All listings and tables will be presented by treatment group.

Safety summaries (tables, figures) include only data from the on-treatment period with the exception of baseline data which will also be summarized where appropriate (e.g. change from baseline summaries). In addition, a separate summary for death including on treatment and post treatment deaths will be provided. In particular, summary tables for AEs will summarize only on-treatment events, with a start date during the on-treatment period (treatment-emergent AEs).

The on-treatment period lasts from the date of first administration of study treatment to 30 days after the date of the last actual administration of any study treatment.

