All information obtained on adverse events will be displayed by treatment group and subject.

Summary tables for AEs will summarize only on-treatment events, with a start date during the on-treatment period (treatment-emergent AEs). The on-treatment period lasts from the date of first administration of study treatment to 30 days after the date of the last actual administration of any study treatment.

The number and percentage of subjects with adverse events and drug-related adverse events will be separately tabulated, by body system and preferred term with a breakdown by treatment. A subject with multiple adverse events within a body system is only counted once towards the total of this body system and treatment.

In addition, the number and percentage of subjects with adverse events will be tabulated by body system, preferred term, maximum severity with a breakdown by treatment group. A subject with multiple severity ratings for an AE under treatment, is only counted under the maximum rating.

Summary tables to show the frequency of subjects affected, time (in hours) of onset and resolution time (in hours) by treatment (MIJ821 0.16 mg/kg pooled, MIJ821 0.32 mg/kg pooled and placebo) and total, will be provided for AEs of interest (dissociation, amnesia, dissociation and amnesia (together), sedation and vomiting).

For these summary tables of AEs of interest, the following guidelines will be applied:

1. Frequency / time to onset / time to resolution of AEs of interest:
 - Frequency - A subject with multiple AEs with the same preferred term (PT) is counted only once for that PT
 - Time to onset – A subject with multiple events in a preferred term of interest, we are only considering the first instant
 - Time to resolution – A subject with multiple events in a preferred term of interest, we are only considering the maximum of the AE duration

2. For subjects who experienced ‘Dissociation and amnesia’:
 - Time to onset – we will use time to 1st instant (whether it’s dissociation or amnesia)
 - Time to resolution – we will use maximum of the AE duration (whether it’s dissociation or amnesia)

3. Based on the consultation with the clinical team, the following rules for grouping of the AEs of interest were elicited:

AE of interest	Notes
Sedation	See AE grouping below
Dissociation	See AE grouping below + ‘dissociative amnesia’
Amnesia	Any term that includes ‘amnesia’, except for ‘dissociative amnesia’ which falls under ‘Dissociation’

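### The grouped adverse-event-of-interest tables in SAP 7.1.1 appear to merge the weekly and bi-weekly MIJ821 arms at each dose for the whole on-treatment period, leaving no readable by-regimen summary of those events

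*SAP*

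**What the plan says.** The Protocol summary lists this secondary objective: "To assess the safety and tolerability of weekly and bi-weekly infusions of MIJ821". Table 2-1 words the safety objective without naming a regimen: "To assess safety and tolerability, especially dissociative side effects". The protocol glossary defines a treatment arm or group by dose and regimen.

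SAP 7.1.1 (Adverse events) plans summary tables of frequency, time to onset and time to resolution for five groupings: dissociation, amnesia, both together, sedation and vomiting. The columns are "by treatment (MIJ821 0.16 mg/kg pooled, MIJ821 0.32 mg/kg pooled and placebo) and total".

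The same section confines AE summary tables to on-treatment events: "The on-treatment period lasts from the date of first administration of study treatment to 30 days after the date of the last actual administration". Within that period a subject counts once per term, only the first onset is kept, and only the longest duration is kept. A 48-hour window after the first dose applies to interim outputs alone.

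**The concern.** Dissociation is the tolerability question that the protocol singles out, and regimen is one of the things that was randomised. The table built for that question has dose columns but no regimen columns.

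Pooling by dose does no harm while both regimens have had the same treatment, that is, up to the second infusion. Over the full on-treatment period they presumably have not. Whether a subject was ever affected, and how long the longest event lasted, can only rise as active infusions accumulate. A column that mixes two different numbers of active infusions then describes neither regimen. A reader who wants to know whether weekly dosing is tolerated as well as bi-weekly dosing would not find the grouped figures that bear on it.

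**Working it through.** The plan gives no figure to reproduce. The check is a reading of the documents followed by an illustration.

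**Step 1: what 'pooled' means.** Protocol Section 3 gives six arms in Europe and five in the USA, where there is no ketamine arm. Six less placebo and ketamine leaves 6 − 2 = 4 MIJ821 arms. SAP 7.1.1 names two doses and the Protocol summary names two regimens, and 2 × 2 = 4. Weekly plus bi-weekly at one dose is therefore the natural reading, though it is an inference.

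**Step 2: how the regimens differ over time.** Table 8-1 has infusion visits on Days 1, 8, 15, 22, 29 and 36. Section 3 has an infusion at each treatment visit, and Section 6.4 has all arms on the same administration schedule. Six active infusions for weekly arms and three for bi-weekly arms fits this, but the readable text does not define the bi-weekly regimen. The count of three is an assumption.

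**Step 3: whether other outputs supply the figure.**

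- *General AE tables (SAP 7.1.1).* These are by treatment, in preferred-term rows. The Dissociation grouping covers dozens of terms. A subject with two of them is in two rows but is one affected subject, so the rows cannot be added to a grouped count. The readable text plans no onset or resolution times for these tables.
- *Psychotomimetic AE incidence (Protocol 12.5.2).* This is by treatment group, severity and relationship to drug. It gives no times, and its term list is not visible.
- *Listings.* These hold subject-level data by treatment group, not a summary.
- *CADSS (SAP 7.2.2).* This is modelled by treatment and time. In Table 8-1, however, the CADSS on Days 8 to 36 falls at 0 h, before the infusion. The only same-day assessment after an infusion is at 1 h on Day 1. Acute dissociation after the second and later infusions therefore reaches the analysis mainly through AE reports.

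**Step 4: possible size (illustration).** Assume an independent risk p per active infusion, six against three active infusions, and equal arms.

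- Weekly: W = 1 − (1 − p)^6
- Bi-weekly: B = 1 − (1 − p)^3
- Pooled column: (W + B)/2

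For p = 0.10: W = 1 − 0.9^6 = 46.9%, B = 1 − 0.9^3 = 27.1%, pooled = 37.0%, and W − B = 19.8 points. The documents give no value of p for MIJ821, so a range is shown:

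| p (assumed) | Weekly | Bi-weekly | Pooled | Gap (points) |
|---|---|---|---|---|
| 0.05 | 26.5% | 14.3% | 20.4% | 12.2 |
| 0.10 | 46.9% | 27.1% | 37.0% | 19.8 |
| 0.20 | 73.8% | 48.8% | 61.3% | 25.0 |

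Independence matters. If 10% of subjects react at every active infusion and the rest never do, both regimens show 10% and the gap is zero. If risk falls with repeat dosing, the gap lies below the table's values.

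**Step 5: what a pooled count can tell.** Average arm size is 66/6 = 11 (the allocation ratio is redacted), so take 22 subjects at one dose. Ten affected of 22 fits all of these splits (Fisher's exact test):

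- 5/11 v 5/11, p = 1.00
- 8/11 v 2/11, p = 0.03
- 9/11 v 1/11, p = 0.002

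The pooled column cannot tell these apart.

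**Step 6: what splitting would buy.** For the gaps in Step 4, power at two-sided 5% with 8 to 14 subjects per arm is about 9% to 27%. By-arm columns would describe the regimens; they would not test the difference.

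**The case against.** The strongest reply is that this is one supplementary table among several. A reader might infer that the plan cannot answer its tolerability objective at all. The documents do not support that: the by-treatment AE tables, the psychotomimetic AE table, the listings and the CADSS model all bear on it.

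A reader might also infer a breach of Protocol 12.5.2, which states: "All listings and tables will be presented by treatment group". That is not shown. SAP 7.1.1 displays AE information by treatment group and plans by-group tables; the pooled table adds to them.

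The objective joins the two regimens with 'and', names them only in the Protocol summary, and does not call for a formal comparison. The Table 2-1 objective "To assess most effective dose and dosing regimen" is paired with MADRS at 6 weeks, so it concerns efficacy and lends no support here. All this stands. It does not rescue the pooled column, which describes neither regimen.

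It is tempting to size the problem with the 20-30% dissociation rate in Protocol 4.3. That is a rate per subject, for ketamine, and cannot serve as a per-infusion risk for MIJ821. The same section reports dissociative effects attenuating with repeat dosing, which would narrow the gap.

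One might also suppose that onset is counted from the first infusion, so that later events show very long onset times. The SAP states no time origin, so this cannot be said.

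Finally, much is redacted, including detail of the first interpretable results, the analysis relating dissociative and amnesia AEs to MADRS, and the graphics. By-regimen output may exist there. Arms are small, and pooling by dose in a non-confirmatory study is a defensible descriptive choice. That argues for keeping the pooled columns, not for having only those.

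**Conclusion.** The point holds in a limited form. In the readable text, the grouped events of interest have no by-regimen summary of frequency, onset or resolution over the on-treatment period, and the other outputs fill the gap only in part. Pooling is sound before the second infusion.

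The conclusion rests on two inferences: that 'pooled' merges the regimens, which is close to forced by the arm count, and that the regimens differ in active infusions after Day 1.

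The size is unknown. Under the assumptions in the working, the pooled column would hide a gap of 12 to 25 percentage points for per-infusion risks of 5% to 20%; under other plausible assumptions the gap is smaller or zero. The table as planned could not show which case applies. This is a worthwhile, inexpensive correction to a descriptive table. It does not touch the primary analysis.

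**What to change.** In SAP 7.1.1, keep the pooled dose columns for events starting before the second infusion (Day 8, 0 h). For the whole on-treatment period, add one column for each randomised MIJ821 arm (dose by regimen), with the same groupings and the same counting rules for frequency, onset and resolution. If a redacted section already contains this output, a cross-reference is enough.

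The cost is SAP wording and programming, with no new data. The drawback is small counts in each arm, so the SAP should say that the by-arm columns are descriptive and do not test one regimen against the other.

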Dissociation and Amnesia	Patients who experienced both amnesia and dissociation

	Applicant grouped:	We added:
Sedation	sedation; somnolence; altered state of consciousness; depressed level of consciousness; hypersomnia; stupor	loss of consciousness
Dissociation	dissociation; depersonalization/derealization disorder; derealization; dissociative disorder; flashback; hallucination; auditory hallucination; visual hallucination; illusion; somatic hallucination; hyperacusis; tinnitus; diplopia; vision blurred; ocular discomfort; photophobia; visual impairment; dysesthesia; oral dysesthesia; paresthesia; paresthesia oral; pharyngeal paresthesia; time perception altered; daydreaming; delusional perception; feeling hot; feeling cold; feeling of body temperature change	dysgeusia; dysmetropsia; feeling abnormal; feeling drunk; hyperesthesia; hypersensitivity; illusion; metamorphopsia; oral hyperesthesia; pharyngeal hypoesthesia; photopsia; photosensitivity reaction; synesthesia; altered visual depth perception; confusional state; delirium; hypogeusia; pain threshold decreased; hypoesthesia; eye hyperesthesia

Separate summaries will be provided for study medication related AEs, SAEs, other significant AEs leading to discontinuation.

In addition, a separate summary for death including on treatment and post treatment deaths will be provided.

For outputs of interim analyses, a safety window of adverse events occurring 48 hours after the 1st injection on Day 1, will be considered. All data for adverse events, as well as time of onset and resolution time for adverse events of interest, will be listed by treatment group and subject,

including non-treatment emergent adverse events and the treatment emergent adverse events occurring 48 hours after first injection on Day 1.

Relationship between dissociative, amnesia AE and MADRS total score

Commercially Confidential Information

ClinicalTrials.gov and EudraCT

For the legal requirements of ClinicalTrials.gov and EudraCT, two required tables on treatment emergent adverse events which are not serious adverse events with an incidence greater than 5% and on treatment emergent serious adverse events and SAE suspected to be related to study treatment will be provided by system organ class and preferred term on the safety set population.

If for a same patient, several consecutive AEs (irrespective of study treatment causality, seriousness and severity) occurred with the same SOC and PT:

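### For AEs of interest, SAP 7.1.1 pairs onset of the first event with the duration of the longest event over up to six infusions, so the two need not describe one episode

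*SAP*

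**What the plan says.** SAP 7.1.1 (Adverse events) plans "Summary tables to show the frequency of subjects affected, time (in hours) of onset and resolution time (in hours) by treatment". The rows are dissociation, amnesia, both together, sedation and vomiting. The columns are two pooled MIJ821 dose groups, placebo and a total. SAP section 2 names a table of the same content among the first interpretable results.

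Three rules cover repeats:

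- Frequency: "A subject with multiple AEs with the same preferred term (PT) is counted only once for that PT".
- Onset: "A subject with multiple events in a preferred term of interest, we are only considering the first instant".
- Resolution: "A subject with multiple events in a preferred term of interest, we are only considering the maximum of the AE duration".

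For the combined row the unit is the patient: "Patients who experienced both amnesia and dissociation". Its onset is the first event of either kind and its duration is the longest of either kind.

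The AE summary tables cover first administration to 30 days after the last. Interim outputs use only the 48 hours after the first dose on Day 1. The general AE table has a rule above preferred-term level: "A subject with multiple adverse events within a body system is only counted once towards the total of this body system and treatment". The visible text gives no matching sentence for the AE-of-interest groups, and no time zero for onset.

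**The concern.** Onset and resolution stand side by side for the same subjects, and a reader will take them as the start and end of a typical episode. For a subject with repeated events they can come from different infusions weeks apart.

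The per-subject maximum also grows with the number of events, even if each episode lasts just as long. A column with more episodes per subject will show longer resolution times for that reason alone. Dissociative side effects are singled out in a secondary safety objective (Protocol Table 2-1), so this is one of the descriptive tables that will be read closely.

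A further problem does not depend on repeat infusions. Each group pools many terms that can overlap in time, and the duration of the longest one is not the time until the whole group of symptoms has gone.

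**Working it through.** The documents give no figure for this point, so there is none to reproduce.

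**Inputs from the documents**

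- Infusion visits: Protocol Table 8-1 has pre-dose columns on Days 1, 8, 15, 22, 29 and 36, which makes six.
- Dissociation terms (SAP 7.1.1): 28 + 20 listed, less 1 listed twice (illusion), plus dissociative amnesia = 48. Sedation: 6 + 1 = 7.
- Regimens: weekly and bi-weekly (Protocol summary). The arms are redacted.

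**Assumptions**

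- Three active infusions for a bi-weekly arm.
- At most one event per infusion, with probability p, equal and independent across infusions. The range is p = 0.05 to 0.50. The only rate in the documents is 20-30% of subjects on ketamine (Protocol 4.3), which is per subject and serves only to place the range.
- Durations exchangeable and, for the ratio, exponential.

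**Formulas.** Let K be the number of infusions with an event, binomial(n, p), among subjects with K ≥ 1.

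- P(first event is also the longest | K = k) = 1/k.
- Expected maximum ÷ expected single duration | K = k: 1 + 1/2 + … + 1/k, which is 1.5 for two events, 1.83 for three and 2.45 for six.

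**Worked case, n = 6, p = 0.20.** P(K = 0) = 0.8^6 = 0.262, so 0.738 of subjects are affected. P(K = 1 to 6) = 0.3932, 0.2458, 0.0819, 0.0154, 0.0015, 0.0001.

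- Same event: (0.3932 + 0.2458/2 + 0.0819/3 + 0.0154/4 + …)/0.738 = 0.742.
- Maximum ratio: (0.3932×1 + 0.2458×1.5 + 0.0819×1.833 + 0.0154×2.083 + …)/0.738 = 1.284.

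**Results among affected subjects**

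| n | p | Two or more events | Onset and duration from same event | Maximum ÷ single |
|---|---|---|---|---|
| 6 | 0.05 | 12% | 94% | 1.07 |
| 6 | 0.10 | 24% | 87% | 1.13 |
| 6 | 0.20 | 47% | 74% | 1.28 |
| 6 | 0.30 | 66% | 62% | 1.45 |
| 6 | 0.50 | 90% | 40% | 1.79 |
| 3 | 0.20 | 21% | 89% | 1.11 |
| 3 | 0.30 | 33% | 83% | 1.18 |
| 1 | any | 0% | 100% | 1.00 |

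The shift differs between columns. With six infusions and the same duration per episode, a column at p = 0.20 would show a mean 1.284/1.065 = 1.21 times that of a column at p = 0.05.

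**Overlapping terms within one infusion.** Suppose one term runs from 0.5 to 1.0 h after the start of infusion and another in the same group from 0.8 to 2.0 h. The longest single AE lasts 2.0 − 0.8 = 1.2 h. The symptoms clear at 2.0 h, which is 1.5 h after they began. Here the rule gives too short a time, so the error can go either way.

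**Time zero.** A first event 0.5 h after the Day 15 infusion has onset 0.5 h if counted from that infusion, or 14 × 24 + 0.5 = 336.5 h if counted from first dose. The visible SAP text does not say which.

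**The case against.** A reader might infer that the table over-counts affected subjects, because repeats are removed only within a preferred term while dissociation pools 48 terms. The documents do not support that. The statistic is defined as subjects affected, the combined row counts patients, and nothing says preferred-term counts are added into a group row. If the row counts subjects, the over-count factor is 1.0. If counts were added, it would equal the mean number of terms per affected subject. The text is silent, which is a gap in detail and not a stated error.

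A reader might also infer that the table describes no real episode. That is too strong. The pair matches for everyone with a single event and whenever the first event is the longest, which is most affected subjects up to p = 0.30 in the calculation above.

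Other defences have weight. The maximum is a conventional worst-case summary, and the SAP states it openly. Outputs limited to 48 hours after the first dose hold one infusion, so mixing across infusions largely disappears there. Protocol 4.3 reports that ketamine's dissociative effects lessened with repeat dosing. If that held here, there would be fewer repeats, the first event would more often be the longest, and the figures above would be too high. Onset and resolution times are also listed by subject, so episodes can be recovered. Redacted text may contain a further rule, and the study is non-confirmatory.

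These points limit the size of the problem but leave the stated rule in place for the full on-treatment table. The listings do not correct the summary, and the 48-hour window does not resolve the overlapping terms.

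**Conclusion.** The concern holds in a limited form. Over the full on-treatment period, the SAP takes onset from the first event and resolution from the longest one. For subjects with events after more than one infusion, the two need not belong together. With six infusions and assumed per-infusion risks of 0.05 to 0.30, they come from different events in about 6% to 38% of affected subjects, and the reported duration averages about 1.07 to 1.45 times a single event. These sizes rest on independent, equally likely events and exponential durations. In addition, the longest single AE is not the time to clearance when terms in a group overlap.

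The documents do not show that subjects are over-counted. Nor do they say that this table determines how long subjects are observed: the protocol sets the observation period without reference to it. The change is a cheap improvement to a named safety table and does not affect the primary analysis.

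**What to change.** In SAP 7.1.1, for each AE-of-interest group and each infusion:

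- Define onset as the earliest start of any term in the group, and resolution as the latest end of those terms, both measured from the start of that infusion. Treat ongoing events as censored.
- Report infusion 1 for all subjects as the main table, with later infusions separately or combined.
- Keep the per-subject maximum duration as an extra column labelled as a worst case.
- State that each subject counts once per group.

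The cost is SAP wording and more programming. With about 66 subjects, five AE categories and up to six infusions, rows for later infusions will be sparse, and combining them limits this. Earliest start to latest end also spans any symptom-free gap between terms after the same infusion. That is acceptable for a time to clearance, but a footnote should say so.
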